3.8.2. Definition Analysis Visit Windows

Subject visits might not occur on protocol-specified days. Therefore, for the purpose of analysis, observations will be assigned to analysis windows.

In general, the baseline value will be the last nonmissing value on or prior to the first dosing date of study drug. For imaging the data, baseline will be the first nonmissing value from screening up to first dosing date plus 4 weeks.

Selected safety and efficacy data collected up to and including the last dosing date plus 30 days (or 42 days for imaging data) will be mapped according to the following analysis windows. Early termination (ET) or follow-up (FU) will use the nominal visit name.

Table 3-1. Analysis Visit Windows for Vital Signs Including Weight, Chemistry, Hematology, Coagulation Labs, Lipid Profile, and Pooled Cohort Score and Risk

Analysis Visit	Study Day	Lower Limit	Upper Limit
Baseline/Day	1	NA	1
Week 1	8	2	18
Week 4	29	19	42
Week 8	57	43	70
Week 12	85	71	> 85

NA = not applicable

Table 3-2. Analysis Visit Windows for FibroSure/FibroTest, CK-18, ELF (and its components), Free Fatty Acid, C-Reactive Protein, ApoA1, ApoB, and Bile Acids

Analysis Visit	Study Day	Lower Limit	Upper Limit
Baseline/Day	1	NA	1
Week 1	8	2	18
Week 4	29	19	56
Week 12	85	57	> 85

Table 3-3. Analysis Visit Windows for Insulin and HOMA-IR

Analysis Visit	Study Day	Lower Limit	Upper Limit
Baseline/Day	1	NA	1
Week 4	29	2	56
Week 12	85	57	> 85

Table 3-4. Analysis Visit Windows for Waist Circumference, ECG, HbA1c, and QoL-Questionnaire

Analysis Visit	Study Day	Lower Limit	Upper Limit
Baseline/Day	1	NA	1
Week 12	85	2	> 85

Table 3-5. Analysis Visit Windows for FibroScan, MRE, and MRI-PDFF

Analysis Visit	Study Day	Lower Limit	Upper Limit
Baseline/Day	1	NA	29
Week 12	85	30	> 85

Data relating to unscheduled visits may be assigned to a particular visit or time point. The following conventions will be followed:

- An unscheduled visit prior to the first dosing of study drug will be included in the calculation of the baseline value.
- For subjects who prematurely discontinue from the study, early termination (ET) data will be summarized as a separate visit, labeled as “Early Termination Visit”
- Data collected on a follow-up visit will be summarized as a separate visit, and labeled “Follow-up Visit.”

3.8.3. Selection of Data in the Event of Multiple Records in an Analysis Visit Window

Depending on the statistical analysis method, single values may be required for each analysis window. For example, change from baseline by visit usually requires a single value, whereas a time-to-event analysis would not require 1 value per analysis window.

If multiple valid, nonmissing, continuous measurements exist in an analysis window, records will be chosen based on the following rules if a single value is needed:

- In general, the baseline value will be the last nonmissing value on or prior to the first dosing date of study drug, unless specified differently. If multiple measurements occur on the same day, the last nonmissing value prior to the time of first dosing of study drug will be considered as the baseline value. If these multiple measurements occur at the same time or the time is not available, the average of these measurements (for continuous data) will be considered the baseline value.

- For postbaseline values:
- The record closest to the nominal day (the nominal day for Week x is Day $7x + 1$) for that visit will be selected.
- If there are 2 records that are equidistant from the nominal day, the later record will be selected.
- If there is more than 1 record on the selected day, the average will be taken, unless otherwise specified.

If multiple, valid nonmissing, categorical measurements exist in an analysis window, records will be chosen based on the following rules if a single value is needed:

- For baseline, the last available record on or prior to the date of the first dose of study drug will be selected. If there are multiple records with the same time or no time recorded on the same day, the value with the lowest severity will be selected (eg, normal will be selected over abnormal for safety electrocardiogram [ECG] findings).
- For postbaseline visits, if there are multiple records with the same time or no time recorded on the same day, the value with the highest severity within the window will be selected (eg, abnormal will be selected over normal for safety ECG findings).

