- 16) Unstable cardiovascular disease as defined by any of the following:
  - a) Unstable angina within 6 months prior to Screening
  - b) Myocardial infarction, coronary artery bypass graft surgery or coronary angioplasty within 6 months prior to Screening
  - c) Transient ischemic attack or cerebrovascular accident within 6 months prior to Screening
  - d) Obstructive valvular heart disease or hypertrophic cardiomyopathy
  - e) Congestive heart failure;
- 17) Use of prohibited concomitant medications as described in Section 5.4
- 18) History of a malignancy within 5 years prior to Screening with the following exceptions:
  - a) Adequately treated carcinoma in situ of the cervix
  - b) Adequately treated basal or squamous cell cancer or other localized non-melanoma skin cancer;
- 19) Any laboratory abnormality or condition that, in the investigator's opinion, could adversely affect the safety of the subject or impair the assessment of study results;
- 20) Participation in another investigational study of a drug or device within 28 days prior or within 5 half-lives of the prior investigational agent (whichever is longer) prior to Screening;
- 21) Concurrent participation in another therapeutic clinical study;

- 22) Known hypersensitivity to GS-0976, the metabolites, or formulation excipient;
- 23) Presence of any condition that could, in the opinion of the investigator, compromise the subject's ability to participate in the study, such as history of substance abuse or a psychiatric (including any subjects with a psychiatric hospital admission or emergency room visit in the 2 years prior to Screening) or medical condition;
- 24) Unavailable for follow-up assessment or concern for subject's compliance with the protocol procedures;
- 25) Contraindications or inability to complete MRI scanning (e.g. presence of permanent pacemakers, implanted cardiac devices, weight restrictions, etc.).

Subjects with laboratory abnormalities outside of the above parameters may be approved for inclusion in the trial with approval from the Medical Monitor.

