#### **6.4.5.            Unscheduled Visit**

Additional unscheduled assessments may be performed at the discretion of the investigator.

Subjects returning to the clinic for an unscheduled visit should be instructed to fast (no food or drink, except water), starting from midnight (00:00) or earlier, as appropriate, on the evening prior to the visit to ensure an approximate 8-hour fast prior to the blood sample collection under fasting condition the next morning.

Subjects should also be instructed to HOLD their dose of study drugs on the day of an unscheduled visit until all visit procedures have been completed. The study drugs should be taken after the visit.

At a minimum, the following will be performed and documented.

- Symptom driven physical examination
- Obtain blood samples for:
  - Chemistry
  - Hematology
- Record body weight
- Record all concomitant medications that the subject has taken since the previous visit
- Record any serious adverse events and all adverse events occurring since the previous visit

If the Unscheduled visit is performed for the sole purpose of distribution of study drug, the assessments noted above do not need to be performed.

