#### **6.8.8. FibroScan®**

The sites will perform liver stiffness assessments by FibroScan®. It is required that each subject have the FibroScan® assessments done with the same type of probe at Baseline Day 1 and Week 12 visits (if available).

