6.2.4. Imaging Data Repeat Scan and Re-read

For MRI-PDFF and MRE data, if a patient has an analyzable repeat scan, then only repeat scan for that visit will be used for analysis. For MRE data, if a patient has a re-read result, then the re-read result for that visit will be used for analysis.

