6.3. Subgroup Analysis of the Efficacy Endpoints

Subgrouping of subjects based on randomization stratification factors will be explored as follows:

- presence of diabetes mellitus
- absence of diabetes mellitus

Descriptive statistics for the above subgroups will be presented for the baseline values, values at each postbaseline visit, change from baseline, and percent change from baseline by visit for MRE and MRI-PDFF.

For each subgroup, the proportion of subjects with at least 30% reduction in MRI-PDFF at Week 12 and the proportion of subjects with at least 15% reduction in MRE at Week 12 will be reported for each treatment group by using a point estimate and 95% CI of the proportion

based on the Clopper-Pearson method. The 95% CI for the difference in proportion between GS-0976 and Placebo will also be provided.

Within each subgroup, the change from baseline of MRI-PDFF and MRE at Week 12 will be analyzed by using an ANCOVA model, with treatment group, and baseline MRI-PDFF or MRE as covariates. For change from baseline, LS means and 95% CIs of LS means will be reported for each treatment group. For treatment differences (GS-0976 – Placebo) of changes from baseline of MRI-PDFF or MRE at Week 12, LS means and 95% CIs will be reported.

Mean (SD) of the observed change from baseline value will be plotted using a line plot by treatment group and visit for subjects from each subgroup.

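### The imaging baseline window stays open to Day 29 on drug, so a subject with no usable pre-dose scan can be given an on-treatment baseline; the effect is probably small, but the rule should be closed and counted

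*SAP*

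**What the plan says.** SAP section 3.8.2 sets a separate baseline rule for imaging: "For imaging the data, baseline will be the first nonmissing value from screening up to first dosing date plus 4 weeks". Table 3-5 applies it to FibroScan, MRE and MRI-PDFF: the baseline window has no lower limit and ends at Day 29, and the Week 12 window begins at Day 30. Tables 3-1 to 3-4, for all other measures, end the baseline window at Day 1.

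Three other SAP rules bear on the point:

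- The general rule in section 3.8.3 is that "the baseline value will be the last nonmissing value on or prior to the first dosing date of study drug, unless specified differently". The closing condition makes it give way to the imaging rule.
- The convention for unscheduled visits in section 3.8.2 is that "An unscheduled visit prior to the first dosing of study drug will be included in the calculation of the baseline value". It does not mention imaging.
- For MRI-PDFF and MRE, section 6.2.4 says that "if a patient has an analyzable repeat scan, then only repeat scan for that visit will be used for analysis". It does not say whether a repeat baseline scan must precede dosing.

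The baseline feeds the change and percent change in section 6.2.2. In section 6.3 it feeds the ANCOVA, "the proportion of subjects with at least 30% reduction in MRI-PDFF at Week 12", and the matching 15% criterion for MRE.

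**The concern.** A baseline should describe the subject before treatment. Here a value taken after as much as four of the twelve treatment weeks can stand in for it. If the drug has begun to act, part of its effect is already in the denominator. The measured fall is then too small in an active-arm subject, while a placebo subject is unaffected in expectation. The treatment difference is pulled toward zero, and the visible SAP has no flag, count or sensitivity analysis that would reveal it.

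The 30% MRI-PDFF response is the endpoint that Protocol section 1.3.1 singles out as important, and the power statement in SAP section 1.3 is built on it.

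**Working it through.** **Is Day 29 a slip?** No. Under the study-day formula in SAP section 3.8.1, first dose plus 28 days is Day 28 + 1 = 29. Text and table agree.

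**The plan's own figure.** SAP section 1.3 gives 80% power for 4% of 25 against 32% of 50 with a two-sided Fisher test. Exact enumeration gives 80.3% with the doubled one-sided p-value and 85.0% with the p-value summed over tables no more likely than the one observed. The 80% is reproduced, and nothing below depends on it.

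**Who can be affected?**

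- *MRI-PDFF and MRE.* Both are scheduled at Screening for every subject, and none is scheduled again until Week 12 or early termination (Protocol Appendix 2). An on-drug baseline needs an unusable Screening scan and an unscheduled scan by Day 29. Protocol section 6.4.5 leaves room for the latter: "Additional unscheduled assessments may be performed at the discretion of the investigator".
- *FibroScan.* There is no Screening measurement and one scheduled pre-dose measurement, on Day 1, where the device is available. If that is missed, an unscheduled measurement by Day 29 could become baseline.
- *Repeat scans.* If section 6.2.4 overrides section 3.8.2, an on-drug repeat by Day 29 could displace a valid Screening scan. Under section 3.8.2 alone the earlier scan is kept. The SAP does not say which rule governs.

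**Effect in one subject.** Let R be the true fall from the pre-dose value by Week 12, and f the share of it present at the late baseline scan. Late baseline = B(1 − fR) and Week 12 value = B(1 − R), so

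measured fall = 1 − (1 − R)/(1 − fR).

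To be counted as a responder at cut-off c, the subject needs a true fall of at least c/[1 − (1 − c)f].

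The documents do not give f. Assume first a linear effect over 84 days, f = (scan day − 1)/84:

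| Baseline scan | f | True 30% PDFF fall reads as | True fall needed for 30% | True 15% MRE fall reads as | True fall needed for 15% |
|---|---|---|---|---|---|
| Day 8 | 1/12 | 28.2% | 31.9% | 13.9% | 16.1% |
| Day 15 | 1/6 | 26.3% | 34.0% | 12.8% | 17.5% |
| Day 29 | 1/3 | 22.2% | 39.1% | 10.5% | 20.9% |

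Example: R = 0.30, f = 1/3 gives 1 − 0.70/0.90 = 22.2%. If one half or two thirds of the effect were present by Day 29, a true 30% PDFF fall would read as 17.6% or 12.5%.

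**Effect on an arm.** Take the SAP's 32% responder rate in 50 subjects. Assume that percent fall is normal with an SD of 15 to 30 points, centred so that 32% reach a 30% fall (an implied mean fall of about 23 to 16 points), and f = 1/3. An affected subject then needs a true fall of 39.1% and responds with probability 14.1% (SD 15) to 22.0% (SD 30). With k subjects affected, the arm rate is [(50 − k) × 32% + k × p]/50:

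| k of 50 | SD 15 | SD 30 | Loss in points |
|---|---|---|---|
| 1 | 31.6% | 31.8% | 0.2 to 0.4 |
| 3 | 30.9% | 31.4% | 0.6 to 1.1 |
| 5 | 30.2% | 31.0% | 1.0 to 1.8 |

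**The case against.** The rule protects itself in nearly every case. It takes the first value from screening onward, so any usable pre-dose scan wins. Screening MRI is required of all, and "Contraindications or inability to complete MRI scanning" is an exclusion (Protocol section 4.3). Early-termination data keep their own visit label, so a scan at early withdrawal does not become baseline. This stands, and it is why the reach is narrow.

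The unscheduled-visit convention can also be read as admitting only pre-dose visits to any baseline. On that reading an unscheduled on-drug scan never qualifies. But the imaging rule is the more specific one and expressly runs past first dose, so the text supports either reading. That is a reason for clarification and for moderate rather than high confidence.

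The direction rests on a drug effect by the late scan. The documents give only a 71% mean inhibition of fractional de novo lipogenesis after one 20 mg dose (Protocol section 1.3.1). They report no four-week effect on fat fraction or stiffness. The direction is most plausible for MRI-PDFF; for MRE and FibroScan an effect by Day 29 is purely an assumption.

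The present rule also keeps more subjects in the analysis, and any bias would run against the drug. Efficacy is exploratory without formal testing (Protocol section 8.5, SAP section 3.5). The redacted SAP sections 6.1 and 6.2.1 may hold a further rule. All of this limits the severity.

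A reader might infer that the Day 29 window biases the imaging results at large, or costs the trial power. The documents do not support that: they show no affected subject, and the extension is idle wherever a pre-dose scan exists. Nor do they support a claim about FibroScan response, since no FibroScan responder definition is visible.

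**Conclusion.** The point holds in a limited form. The SAP permits an on-drug imaging baseline up to Day 29 when no usable pre-dose value exists, and it leaves unclear whether unscheduled or repeat scans may supply it. If the drug has acted by then, change is understated in that active-arm subject, and for MRI-PDFF and MRE so is response.

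For one subject the distortion can matter: at Day 29 under a linear effect, a true PDFF fall between 30% and 39.1% is lost as a response. For an arm it is about 0.2 to 1.8 points on a 32% rate, given one third of the effect present and 1 to 5 of 50 affected. Those counts are illustrative; the documents give none, and few subjects are likely. Severity is minor, confidence moderate.

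**What to change.** - In SAP section 3.8.2 and Table 3-5, close the imaging baseline window at first dose for the main analysis, and treat baseline as missing where there is no pre-dose value.
- In section 6.2.4, let a repeat replace a baseline scan only if the repeat is also pre-dose.
- Report the number of subjects with an on-drug baseline, by arm and modality.
- Keep the Day 29 window as a labelled sensitivity analysis.

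If nobody is affected, no result changes and the report can say so.

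**Cost.** The change needs new wording, one count table and one extra run. Subjects without a pre-dose value leave the main analysis of that modality. The confidence interval for an active-minus-placebo mean difference scales with √(1/n_active + 1/n_placebo), assuming a common SD. Against 50 and 25, with placebo losses in proportion and rounded down or up:

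| Active subjects lost | Group sizes | Widening |
|---|---|---|
| 1 | 49/25 or 49/24 | 0.3% or 1.7% |
| 3 | 47/24 or 47/23 | 2.4% or 3.9% |
| 5 | 45/23 or 45/22 | 4.6% or 6.2% |

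No gain in power is claimed.

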biochemistry (e.g. ALT and GGT); noninvasive serum markers of liver injury (e.g. serum CK-18, FibroTest® and ELF™ Test); and imaging-based methods for quantifying hepatic steatosis (MRI-PDFF) and fibrosis (MRE and FibroScan®). An important endpoint of interest is the proportion of subjects achieving  $\geq 30\%$  reduction in steatosis as assessed by MRI-PDFF. This level of reduction has been associated with a significant improvement in NASH histology ( $\geq 2$ -point reduction in NAFLD Activity Score) {Patel 2015}. Based on preclinical and clinical data, a treatment duration of 12 weeks with GS-0976 is expected to be sufficient to lead to meaningful improvements in hepatic steatosis on MRI-PDFF and liver biochemistry. Liver histology has not been included as an endpoint because it is not feasible to repeat this invasive procedure over a 12-week study. In addition to these liver-related endpoints, the effects of GS-0976 on carbohydrate and lipid metabolism (e.g. with glucose, insulin, free fatty acids, apolipoproteins, lipid profiles, and metabolites) will be closely monitored in light of the mechanism of action of GS-0976 and the importance of metabolic dysfunction in contributing to the morbidity and mortality (e.g. cardiovascular) of subjects with NASH.

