#### **6.4.4. Week 12 Visit ( $\pm 7$ days)**

Subjects should be instructed to fast (no food or drink, except water), starting from midnight (00:00) or earlier, as appropriate, on the evening prior to the Week 12 visit to ensure an approximate 8-hour fast prior to the fasted blood sample collection the next morning.

Subjects should also be instructed to HOLD their dose of study drugs on the day of their Week 12 visit until all visit procedures have been completed. The study drugs should be taken after the visit.

The following will be performed and documented at this visit ( $\pm 7$  days):

- QoL Questionnaires (SF-36, WPAI, and CLDQ)
- Symptom driven physical examination

- Record vital signs, waist circumference, and body weight
- Obtain blood samples for:
  - Chemistry
  - Hematology
  - Coagulation Panel
  - Lipid Profile
  - Hemoglobin A1c
  - Biomarker
  - Single PK sampling
- Collect urine samples for:
  - Urine pregnancy test for females of child bearing potential only
  - Biomarkers
- Conduct standard 12-Lead ECG
- Perform FibroScan® (if available)
- Perform MRE and MRI-PDFF
- Collect stool sample for Biomarkers (see Study Reference Binder for instructions)
- Record all concomitant medications that the subject has taken since the previous visit
- Record any serious adverse events and all adverse events occurring since the previous visit
- Review of study drug dosing compliance (pill count)

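### SAP 3.8.2 lets scans taken up to 42 days after the last dose count as Week 12; add a paired analysis limited to scans taken near the last dose

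*SAP*

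**What the plan says.** SAP 3.8.2 admits to the analysis windows "Selected safety and efficacy data collected up to and including the last dosing date plus 30 days (or 42 days for imaging data". The table headed "Table 3-5. Analysis Visit Windows for FibroScan, MRE, and MRI-PDFF" sets the Week 12 window from Day 30 to beyond Day 85, with nominal Day 85 and no upper study-day limit. For imaging, the 42-day rule is therefore the only cap.

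Three other rules bear on which scan is used:

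- **Labels (SAP 3.8.2).** "Early termination (ET) or follow-up (FU) will use the nominal visit name", and for subjects who leave the study early "early termination (ET) data will be summarized as a separate visit".
- **Several records in one window (SAP 3.8.3).** "The record closest to the nominal day" is selected.
- **Repeat scans (SAP 6.2.4).** For MRI-PDFF and MRE, "if a patient has an analyzable repeat scan, then only repeat scan for that visit will be used for analysis". That section states no time limit for the repeat.

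Protocol 6.4.4 lists MRE, MRI-PDFF and (if available) FibroScan among the Week 12 procedures under the words "The following will be performed and documented at this visit", with a tolerance of ± 7 days. That day's dose is held only until the procedures are finished. Protocol 1.3.1 gives the expectation behind the timing: "a treatment duration of 12 weeks with GS-0976 is expected to be sufficient to lead to meaningful improvements in hepatic steatosis on MRI-PDFF".

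**The concern.** The protocol intends the Week 12 scan to be taken about one day after the previous dose. The SAP accepts a scan up to six weeks after the last dose under the same label, and the visible text gives no reason for 42 days. In these cases the visit label and the 42-day cap, not whether the subject was still on drug, decide what counts as Week 12.

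If liver fat or stiffness moves back once the drug has gone, only the active arms have a drug effect to lose, so any bias would run toward no difference. The outputs exposed are the Week 12 changes in PDFF and MRE and the proportion with at least a 30% PDFF reduction. SAP 6.3 reports these by diabetes subgroup with confidence intervals for the comparison with placebo, and the PDFF response is the endpoint in the power statement of SAP 1.3. A responder cut-off is sensitive to this, because a modest return can move a subject across it.

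**Working it through.** **1. How late can a Week 12 scan be?** With a last dose on Day 84 or 85, the cap is 84 + 42 = Day 126 or 85 + 42 = Day 127. The protocol visit window is Day 85 ± 7, that is Day 78 to 92. The last scheduled visit, Follow-Up, is 28 ± 5 days after the last dose, at most 33 days, and has no imaging (Protocol 6.4.6 and Appendix 2).

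**2. Is the drug gone by then?** Mean half-lives run from 3.5 h (Protocol Table 1-2) to 11.7 h (Table 1-1). Five half-lives are 17.5 to 58.5 h, or 0.7 to 2.4 days. At 11.7 h the fraction left after 72 h is 2^(−72/11.7) = 1.4%. Forty-two days is 1008 h, or 1008/11.7 ≈ 86 to 1008/3.5 = 288 half-lives. These are plasma values from Phase 1 studies in healthy subjects at 30 mg or more, not from NASH subjects at 5 or 20 mg.

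**3. Which off-drug scans can reach Week 12?**

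- A single late or unscheduled scan, with no competing record nearer Day 85.
- A repeat scan, since SAP 6.2.4 lets it replace an on-drug scan at the visit.
- A Week 12-labelled scan in a subject who stopped drug but stayed in the study, as Protocol 5.1.1 foresees after unblinding. If such a subject stops on Day 50, a scan on Day 85 (35 days off drug) counts and one on Day 95 (45 days off) does not.

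Scans labelled early termination or Follow-Up do not enter.

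**4. The plan's own figure.** SAP 1.3 states 80% power for 4% (n = 25) versus 32% (n = 50), two-sided Fisher's exact test at 0.05. Exact enumeration, with the two-sided p-value taken as twice the smaller tail, gives 80.3%; the Walters arcsine approximation with continuity correction gives 80.0%. The figure reproduces. (Summing the small probabilities instead gives 85.0%.)

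**5. Responder difference, under assumptions.** Let a share f of 20 mg Week 12 scans be off drug and lose a share l of the responder effect. Then p = 0.32 − f × l × 0.28, and the difference is p − 0.04. Neither f nor l is in the documents.

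| f | l | Difference (points) | Power |
|---|---|---|---|
| 0 | any | 28.0 | 80.3% |
| 5% | 50% | 27.3 | 78.2% |
| 5% | 100% | 26.6 | 76.0% |
| 10% | 50% | 26.6 | 76.0% |
| 10% | 100% | 25.2 | 71.2% |
| 20% | 50% | 25.2 | 71.2% |
| 20% | 100% | 22.4 | 60.4% |

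If l = 0, nothing changes for any f.

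**6. Mean effect, under assumptions.** Suppose the effect decays off drug with a half-time h of 2 to 6 weeks (assumed).

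- At exactly six weeks, 2^(−6/2) = 12.5% to 2^(−6/6) = 50% remains.
- For scans spread evenly over 0 to 6 weeks, the mean share remaining is h/(6 ln 2) × (1 − 2^(−6/h)): 42% for h = 2 and 72% for h = 6, a loss of 58% or 28%. If 10% of active-arm scans are late (assumed), the mean effect is understated by 0.10 × 28% to 0.10 × 58%, about 3 to 6%.
- A subject with a 40% reduction on drug falls below 30% after h × log2(40/30), which is 0.8 weeks (h = 2) to 2.5 weeks (h = 6).

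**7. What would excluding late scans do to power?** With the same Fisher convention, 24 versus 48 scans (about 4% lost) gives 77.5%, and 22 versus 45 (about 10% lost) gives 73.0%. Full loss of effect at f = 5% and 10% gives 76.0% and 71.2%. Exclusion therefore costs about as much power as full dilution. What it can buy is less bias.

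**The case against.** Plasma clearance is not loss of effect on a tissue measure. The documents give no rate at which liver fat or stiffness returns after stopping, and they describe the drug as extracted by and directed to the liver (Protocol 1.2.4 and 1.3). For MRE and FibroScan there is not even an assumed rate to work with. This stands: dilution is possible, not shown.

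The route is also narrow. An on-schedule Week 12 scan is essentially on drug, no imaging is scheduled at Follow-Up, and the record nearest Day 85 is preferred. Subjects stopping treatment are sent to the Week 12/ET procedures (Protocol Appendix 2, note b), and the SAP keeps early termination data separate for those who leave the study. A reader might infer that all imaging within 42 days of the last dose becomes Week 12; the labelling rules do not support that. The routes in step 3 remain open.

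Using every available scan is a legitimate choice. Dropping late scans selects on something that happens after randomisation, and the dropped values become missing in a Full Analysis Set for which SAP 3.6.1 generally plans no imputation. This stands against making a tighter window the only analysis, but not against a paired one.

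Finally, the primary endpoint is safety, and efficacy is exploratory without formal comparisons (Protocol 8.5). The consequence would be a somewhat shrunken estimate, not a failed test. The model text in SAP 6.2.1 is redacted, so it cannot be said that no sensitivity analysis exists.

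**Conclusion.** The point holds in a limited form. The SAP's imaging rule can place off-drug scans in the Week 12 analysis, against a protocol visit designed to be on treatment, and the repeat-scan rule can substitute one for an on-drug scan. Any resulting bias would plausibly run toward no difference.

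Its size cannot be fixed from the documents. The 25.2 to 26.6 points (from 28) and the 3 to 6% understatement of the mean effect rest on an assumed 10% of late scans and on assumed losses or return rates. With slow or no return, the effect is about zero. A reader might take 5 to 9% as the size of the understatement, but that puts every late scan at the full six weeks (0.10 × 50% to 0.10 × 87.5%). Nor do the documents support stating as fact that the Week 12 effect is diluted.

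This is a cheap improvement to an exploratory analysis, not a flaw that invalidates it.

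**What to change.** Keep the 42-day rule for the analysis of all available scans and give the reason for 42 days. Add to SAP 3.8.2 and 6.2.4:

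1. A pre-specified paired analysis of Week 12 MRI-PDFF and MRE limited to scans no later than last dose + 7 days, shown beside the 42-day result. The 7 days are borrowed by analogy from the Week 12 visit tolerance, which runs around the visit and not from the last dose, so the SAP should call the cut-off a choice.
2. A repeat-scan rule for that analysis: where the repeat falls outside the limit, use the initial analyzable scan if it is inside.
3. A table of days from last dose to Week 12 scan, by arm.

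The table shows whether the issue arose at all; if almost every scan is within a few days of the last dose, the two analyses will agree. The cost is one extra table and slightly fewer scans in the restricted analysis, which should be read as a check on bias and not as a gain in power. If the SAP is already final, its section 1 sends the change to the clinical study report.
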